groups were found on alcohol consumption. For comparing the longitudinal profile of the substance use outcomes (standard drinks/day, peak standard drinks/day, # drinking days, # binge drinking days) using repeated measures analysis assuming 3 measurement time points, level of significance  $\alpha=0.05$ , two-tailed comparison, correlation between pairs of measurements within participants no larger than  $\rho=0.5$ , we estimate that 50 participants per group (total  $n=100$ ) are needed to achieve a power of 89% to detect a difference of 0.5 standard drinks between GMI and CT. A sample size of 65 ( $n=130$ ) will provide 83% power to detect a difference of 0.4 standard drinks between treatment conditions. The corresponding sample size requirements after adjusting for a 30% dropout rate are 142 (71 per group) and 186 (93 per group), respectively. To account for the “fraction of missing” information that must be imputed in the intent-to-treat (ITT) sample and the dilution effect of ITT analyses, we further inflate the sample size by 30% to achieve a final ITT sample size of 93 participants randomized to GMI and CT (total  $N = 186$ ) to detect a difference of 0.4 standard drinks between treatment conditions. For the global statistical test (GST), when the collection of outcomes (e.g., standard drinks/day, etc.) show consistent directionality with regard to improvement, GST will have higher power than that of tests of single outcomes.

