## **C12. Overview of the statistical analysis plan.**

**Effectiveness analyses:** all health services and participant outcomes (see section C9) will be obtained at three time points (month 1, 3 and 6-months post-randomization). These variables include: (a) Substance use outcomes (e.g., standard drinks/day (SEC), peak standard drinks/day, # drinking days, # binge drinking days, # illicit drug use days, etc.); (b) Treatment engagement (e.g. # of substance abuse/mental health treatment sessions attended, # AA sessions attended, # AA sponsor contacts; (c) Psychosocial adjustment (social support, community participation) and (d) Quality of life/psychiatric indices (QOLS, SF-12, BSI-18); (e) Engagement in structured/productive work activities (% of days each month engaged in work or volunteer activities); (c) Process measures (CPOSS-VA, HAQ) will be assessed at 1-month follow up.

**Analysis sets.** The ITT sample comprises all randomized participants. The per-protocol/completer sample comprises participants who are compliant with protocol requirements and for whom all required measurements have been made. Primary analyses will be carried out using the ITT analysis set.

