sensitivity analysis will be made to balance between model complexity and reduction in bias. We will use Poisson distribution with a log-link for count outcomes (e.g., # drinking/drug use days, # days SUD treatment, # days structured work activities), Binomial distribution with logit-link for binary outcomes (e.g. attended treatment/did not attend treatment) and Gaussian distribution with identity-link for continuous outcomes (e.g., standard drinks). When we suspect over-dispersion in the count models that is beyond what is assumed by the Poisson GLMM then we will use Negative Binomial distribution. To deal with zero inflation, we will use zero-inflated Poisson (ZIP) and negative binomial (ZINB) models. For multiple outcomes, we will use a joint model based on linking the GLMM models for each outcome type by assuming a joint statistical distribution for the random coefficients (intercept and slopes). Let  $Y_{ijk}$  be the response from the  $k$ th outcome for subject  $i$  at occasion or time  $j$  ( $i=1, \dots, n$ ;  $k=1, \dots, K$ ;  $j=1, 2, \dots, n_i$ ). The GLMM can be given as,  $E(Y_{ijk} | X_{ij}(t), Z_{ij}) = g^{-1}(X_{ij}(t)\beta_k + Z_i b_{ik})$ , where  $b_{ik} \sim N(0, G_k)$  and  $X_i$  and  $Z_i$  represent vectors of fixed and random effect covariates, respectively, and  $G_k$  is the covariance matrix for  $b_{ik}$ . We will use a random coefficient model with shared random intercept and random slope for each outcome. The resulting 'over all' covariance matrix (D) from this model will provide standard error estimates that account for correlation among the multiple outcomes. A key assumption for these models is conditional independence where the responses are independent given the random effects. These models can be fitted using Proc NLMIXED or GLIMMIX in SAS v9.3.

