**C12d. Analysis plan for Clinical, Social, and Quality of Life outcomes (Specific AIM I; Hypotheses 1 through 4):** To evaluate the relative efficacy of (a) GMI and (b) CT on (a) five health services outcomes (i) substance use (ii) treatment engagement, (iii) psychosocial integration (e.g., social support, community participation), (iv) quality of life/psychiatric indices, and (v) # of days engaging in structured/productive work activities. The longitudinal trajectory of efficacy outcomes will be compared using the GLMM approach, which accommodates missing at random (MAR) data and a wide range of data types/distributional assumptions: counts (e.g., # AA sessions, # times talking with AA sponsor, # substance abuse treatment sessions attended); dichotomous (e.g., abstinent/not abstinent), proportions (proportion days not drinking alcohol or using illegal drugs), and ordinal (e.g. CPOSS-VA, QOLS). When the number of zeroes is in excess of what is normally expected from a poisson model, we will fit GLMM to accommodate zero-inflation. We will use negative binomial regression to deal with over dispersion. Logit link for dichotomous outcomes, log link for count outcomes will be considered. The basic modeling procedure involves using the longitudinal outcome measurements within each of the domains separately as the dependent (outcome) variable, with intervention group (fixed effect), time (random effect), and time by intervention as the primary independent variables. In further multivariable modeling, additional covariables (as appropriate for a given dependent variable) will be added to the basic model to adjust for potential confounding effect of these variables. GLMM accommodates both fixed and time-varying covariates. For example, for the treatment engagement variable, the # of AA sessions measured monthly for 6 months will be an outcome variable, intervention group (GMI, CT), time, and time X intervention will be the primary independent variables in the basic (unadjusted) model, and psychiatric comorbidity (number and severity), age, race, and gender will be added in the subsequent (adjusted) model to adjust for the possible confounding effect of these variables. Unadjusted and covariate-adjusted least squares means for each outcome variable will be compared at the primary time point (month 1) and at intermediate secondary time points (months 3 and 6) using appropriate model contrasts and the Tukey-Kramer adjustment for multiple comparisons for the secondary time points. These contrast comparisons, along with corresponding 95% CI, will provide estimates of the difference in outcome means (effect sizes) for the hypothesized comparisons. For longitudinal dichotomous outcomes (e.g., maintenance of sobriety), we will compare unadjusted and covariate-adjusted proportions across the longitudinal trajectory (at 1, 3 and 6 months) for GMI and CT. For the end-of-active treatment time point, this analysis is equivalent to a logistic regression analysis.

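### Tukey-Kramer does not fit the two planned GMI-CT contrasts at months 3 and 6: within a visit it corrects nothing, and across the four arm-by-visit means it over-corrects

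*Combined protocol and SAP*

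**What the plan says.** C12d fits a mixed model for each outcome "with intervention group (fixed effect), time (random effect), and time by intervention as the primary independent variables". Least squares means "will be compared at the primary time point (month 1) and at intermediate secondary time points (months 3 and 6". For the later visits it uses "appropriate model contrasts and the Tukey-Kramer adjustment for multiple comparisons for the secondary time points", and it takes effect estimates and 95% confidence intervals from the same contrasts.

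The trial has two arms. The overview in C12 says outcomes "will be obtained at three time points (month 1, 3 and 6-months post-randomization". So an outcome measured at every visit has one primary contrast (month 1) and two secondary ones (months 3 and 6).

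C12d does not state the set of means to which Tukey-Kramer applies. It could be the two arm means within a visit, or the four arm-by-visit means at months 3 and 6. C12c deals with multiplicity over outcomes, not over visits, so the C12d sentence is the only rule for the visits. On software, C12c says: "These models can be fitted using Proc NLMIXED or GLIMMIX in SAS v9.3".

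**The concern.** Tukey-Kramer protects all pairwise differences within one set of means. What needs protecting here is narrower: two prespecified differences between arms, one at each later visit.

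A within-visit adjustment does not reach that multiplicity, because each visit offers only one pair. The report could describe results as Tukey-Kramer adjusted when nothing had been adjusted. An adjustment over the four arm-by-visit means does reach it, but also charges for pairs the plan never asks about, such as GMI at month 3 against CT at month 6.

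C12c says that Type I error must be weighed against excessive Type II error. The first reading neglects one side of that balance and the second neglects the other. The results at stake concern durability of effect. The booster session takes place two months after the intervention, so months 3 and 6 are the only assessments that follow it. With the family unstated, the choice could also be made after the data are seen.

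**Working it through.** **The plan's own power figures.** C11 plans for the longitudinal profile "using repeated measures analysis assuming 3 measurement time points", with two-sided alpha 0.05 and within-person correlation of at most 0.5. It gives 89% power with 50 per group for a difference of 0.5, and 83% with 65 per group for 0.4. It states no SD, so I assume SD = 1.

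- With AR(1) correlation 0.5 and three visits, the variance factor for a person's mean is (1/9)[3 + 2(0.5 + 0.5 + 0.25)] = 0.611.
- 0.5/√(2 × 0.611/50) − 1.960 = 1.238, so power is 89.2%.
- 0.4/√(2 × 0.611/65) − 1.960 = 0.957, so power is 83.1%.

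Both stated powers are reproduced. Compound symmetry with four visits comes close (88.5% and 82.2%); with three visits it does not (86.5% and 79.8%). Reading 0.4 as 0.4 SD is therefore consistent with C11, but it remains an assumption. For dropout, 65/0.7 = 92.9, which gives the planned 93 per arm.

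**Critical values.** For k means, the Tukey-Kramer critical value on the t scale is q(0.95; k, df)/√2, where q is the studentized range quantile.

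- k = 2 (one pair): 1.960 for large df and 1.979 at 128 df, the same as the unadjusted test. This is an identity and needs no SD or effect size.
- k = 4 (4 × 3/2 = 6 pairs): 2.569, or 2.603 at 128 df.
- Bonferroni for two contrasts (alpha 0.025 each): 2.241, or 2.268 at 128 df.

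**Error rate over the two planned contrasts.** With independent contrasts and no effective correction it is 1 − 0.95² = 9.75%. A bivariate normal calculation gives 9.1% at correlation 0.5, the ceiling in C11, and 7.8% at 0.8. At a critical value of 2.569 the per-contrast level is 0.0102, so the rate cannot exceed 2 × 0.0102 = 2.04% whatever the correlation.

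**Single-visit power, illustrative.** Power = Φ(δ/√(2/n) − c), where δ = 0.4 SD and c is the critical value. The noncentrality is 0.4/√(2/65) = 2.280 with 65 per arm and 0.4/√(2/93) = 2.728 with 93 per arm.

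| Adjustment | c | Two-contrast error, independent / correlation 0.5 | Power, 65 per arm | Power, 93 per arm |
|---|---|---|---|---|
| None, or Tukey-Kramer within a visit | 1.960 | 9.75% / 9.1% | 62.6% | 77.9% |
| Bonferroni for two contrasts | 2.241 | 4.9% / 4.7% | 51.6% | 68.7% |
| Tukey-Kramer over four means | 2.569 | 2.0% / 1.9% | 38.6% | 56.3% |

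Against the two-contrast correction, the relative loss with four means is 1 − 38.6/51.6 = 25% with 65 per arm and 1 − 56.3/68.7 = 18% with 93 per arm. Noncentral t gives nearly the same picture: 50.7% to 37.7% with 65 per arm (128 df), and 68.0% to 55.5% with 93 per arm (184 df).

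**The case against.** The strongest reply is that neither reading yields an incorrect analysis. Over the arm-by-visit means, Tukey-Kramer keeps the two-contrast error at about 2%, well under 5%. Within a visit, each p-value and 95% interval is right for its own contrast, and only the joint statement over two secondary visits is unprotected. This stands. A reader might infer that the month-3 and month-6 p-values and intervals would be wrong either way, and the documents do not support that.

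A reader might also infer that the adjustment could halve power. That needs the month-1 means in the family. With six means and 65 per arm, c is 2.850 and power is 28.5%, a loss of 45% against the two-contrast correction and 55% against no adjustment. But C12d confines the adjustment to the secondary time points and calls month 1 primary. Running the Tukey option on the whole arm-by-visit table would bring those means in by accident, but the sentence does not call for it.

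The impact is limited in other ways. C11 promises no power for a single visit. Many outcomes are counts for which Poisson or negative binomial models are planned. Not every measure is affected either: Table 4 schedules the satisfaction, alliance and cohesion scales at month 1 only, and the MSVT at baseline and month 3 only.

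These points reduce the size of the problem but do not remove it. On neither reading does the named method match the two contrasts it is meant to cover.

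**Conclusion.** The point holds as a mismatch between the method and the planned contrasts, made worse by an unstated family. The within-visit result is exact: Tukey-Kramer on two means is the unadjusted test. The resulting 9.1% to 9.75% assumes a correlation between the two contrasts of 0 to 0.5. The four-mean result, a critical value of about 2.57 to 2.60 with a two-contrast error near 2%, does not depend on any SD.

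The power figures are illustrative. They assume a 0.4 SD difference although the documents give no SD, a Gaussian outcome, one visit analysed without borrowing from the others, and no clustering by therapy group. On that basis the avoidable loss is roughly 12 to 13 percentage points (51.6 − 38.6 = 13.0 with 65 per arm; 68.7 − 56.3 = 12.4 with 93).

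The month-1 primary contrast lies outside this adjustment, and the C11 calculation does not use it. Neither is affected. The change is worth making, but the trial's primary conclusion does not depend on it.

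**What to change.** In C12d, replace Tukey-Kramer with a single-step correction over exactly two GMI-CT contrasts, month 3 and month 6, for each outcome assessed at both visits. State that the month-1 primary contrast is outside this family. Either of these would serve:

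- Bonferroni: alpha 0.025 for each contrast, with 97.5% confidence intervals. It needs only each contrast's estimate and standard error, so it works with either SAS procedure named in the plan.
- A simulation-based adjustment on those two estimates, which uses their correlation and gives adjusted p-values and simultaneous intervals together.

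Holm could be used for p-values only. It has no simple matching simultaneous intervals, and C12d relies on intervals from these contrasts.

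The cost is one sentence in C12d and a small change to the analysis program, best made before any comparison by arm is seen. No change to sample size, visits or data collection is needed.

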
**C12e. Analysis Plan for Cost Estimation of Intervention (Specific Aim III):**

Descriptive statistics will be used to describe the estimated cost of intervention for Veterans living at various distances from the VAMC where care is provided. Differences in mean VA costs for GMI vs. CT will be estimated. *We will employ GLMM as for the clinical outcomes, to estimate the independent association of Veteran demographic and clinical factors with cost as well as test for sensitivity of cost results across clinical outcomes and workload*. Research economists (if they have access to PHI) will evaluate VINCI health services utilization and cost data up to one year post intervention for all participants in the study. To be consistent with this time period as well as to provide greater methodological rigor to the study, we would like to evaluate a comparison group of Veterans similar to study participants in that they are deemed homeless or have used the homeless clinic.

### **C13. Dissemination/Implementation Plan**

Given positive findings from this study, future dissemination/implementation efforts of GMI within VISN 7 may positively impact a substantial number of Veterans with SUDs in VA housing. Findings from this study will be of interest to administrators and VA mental health professionals in local (e.g., Charleston VAMC), regional, (e.g., VISN 7) and national offices, particularly the National Center on Homelessness among Veterans (NCHAV), VA housing services, Veterans Homelessness Prevention Demonstration Program (VHPD), Mental Illness Research, Education, and Clinical Centers (MIRECC), and Supportive Services for Veteran Families.

#### **C.13a. A systematic plan of five dissemination activities to impact these agencies will involve:**

**1) Presentations, courses, seminars, invited grand rounds, and workshops** describing project results and demonstrating GMI application in VA housing programs starting in Columbia, Alabama, Atlanta, Birmingham, and Tuscaloosa; **(2) Synthesizing and summarizing data for distribution** to relevant stakeholder groups (e.g., NCCHV, VA's within the VISN) using descriptive materials outlining the study and its objectives in the form of white papers and brochures. In-person and Live Meeting presentations will be conducted for NCCHV, HUD-VASH, GPD, MIRECC, and VHPD with the coordination and direction of [name], VISN 7 Network Homeless Coordinator of the VA Southeast Network, [name]. National Director of VHA Clinical Operations of the Homeless Program Office; and [name], HUD-VASH research investigator at Birmingham VAMC. Other presentations and workshops will occur at scientific conferences (e.g., APA, ABCT, CPDD, VA Housing First meetings); **(3) Publication of study results** and brief executive summaries in professional and non-professional outlets (e.g., psychiatric, psychological, medical journals, VA newsletters). The PI will draft publication guidelines within the first three months of the study. An additional responsibility will be development of a standardized dissemination "package" when the primary manuscript is accepted for publication. Such a package might include a model cover letter or memo, a press release, and reprints of the primary manuscript and secondary manuscripts already published; **(4) Contacting and informing the newly created VA Evidence Based Practice EBP representatives** in order to 'get the word out' to practitioners. Nationwide, 3/8 support of a senior clinician at every VAMC has been designated by Central Office for this program. Representatives attend a national conference and work within their VA to enhance dissemination of evidence based clinical strategies; **(5) A social marketing plan** will be assembled by the PI and [name] for launching the seven structured implementation activities below.

**C.13b. A structured plan of seven implementation activities will involve:** **(1) Reviewing data from the study and discussing the implications of study findings among members of the project team** (Drs. [name], [name], [name], and [name]) with reference to immediate relevance to the Housing First initiative. GMI may serve as a key tool and may become a permanent part of the dissemination package within VA housing, designated as an in initial 'wraparound' treatment service in the newly adopted Housing First initiative within VA; **(2) In their VISN level roles, [name] and [name] will set up consultation with [name], National Director of VHA Clinical Operations of the Homeless Program Office, [name], National Director GPD, and [name], Director of NCCHV and for support** with the aim of discussing dissemination throughout VISN 7 and to create a plan of promulgating directives and implementation activities for moving GMI forward; **(3) As the Evidence-Based Training Program Coordinator in VISN 7 and based on the findings of her implementation research, [name] will develop a set of standard operating procedures necessary for creating a successful GMI program, consisting of training tasks, intervention location, patient recruitment tasks, program/administrative support requirements, and treatment monitoring tasks;** **(4) SOP procedures will be disseminated with the assistance of [name], [name], and [name] in each HUD-VASH/GPD program, giving [name] a VISN-wide impact with respect to training and GMI adoption;** **(5) [name] will conduct a series of VISN 7 VA housing site visits** starting in Columbia, Alabama, Atlanta, Birmingham, and Tuscaloosa to evaluate GMI implementation needs, conduct organizational readiness/attitude belief surveys and perceptions of the GMI program to diagnose potential obstacles as necessary, evaluate feasibility, and identify staff/MI leads to enhance program support (these data will be used in a QUERI SDP proposal-see below); **(6) These five tasks will support a GMI VISN 7 initiative** directed by [name] that moves beyond Charleston so that a GMI VA housing program is operating in other locations within the VISN. This will involve a) Staff agreement/adoption; b) GMI staff training; c) identifying MI 'site' leads; and d) disseminating standard operating procedures; **(7) A Service Directed Project (SDP) will be sought** as a potential 'next step' through the Quality Enhancement Research Initiative (QUERI), after evidence for GMI is shown to be substantial, for providing implementation support for translating research into practice.

**Table 6. PROJECT MANAGEMENT PLAN**

| Task Description                                   |   | PI                       | Project Staff | Co-I's               |
|--|---|--------------------------|---------------|----------------------|
| Study Design/Set up                         | Coordinate GMI/CT training  | X                        | X             |                      |
|  | Coordinate IRB submission   | X                        | X             |                      |
|  | Update/Refine GMI protocol/feedback report  | X                        |               | SM                   |
|  | Assemble study team   | X                        |               |                      |
|  | Coordinate study design   | X                        | X             |                      |
|  | Assemble project documents (assessments)  | X                        | X             |                      |
|  | Oversee patient recruitment, consent, retention   | X                        | X             |                      |
|  | Implementation, Formative, Process, & Summative Evaluation  | X                        | X             |                      |
|  | Statistical Analysis  | X                        | X             | CP, MG
MG, RR, LD |
|  | Data Management & Programming  | Set up project databases | X             | X                    |
| Oversee/conduct data cleaning/data checks          |   | X                        | X             |                      |
| Cost estimation                                    |   | X                        |               | RR, LD               |
| Track Formative, Process, and Summative Evaluation |   | X                        |               | CP                   |
| Update therapist fidelity protocol                 |   | X                        |               | SM                   |
| Rate GMI/CT sessions                               |   | X                        | X             | SM                   |
| Oversee therapist adherence/competence data        |   | X                        |               | SM                   |
| Dissemination                               | Oversee development of study materials  | X                        |               | ALL-Co-I             |
|  | Oversee publication of study results in professional/ non-professional outlets                              | X                        |               | ALL-Co-I             |
|  | Oversee development of presentations (invited grand rounds, meetings, workshops) describing project results | X                        |               | ALL-Co-I             |
| Project meetings                            | Lead  | X                        |               |                      |
| Project budget                              | Ongoing budget review   | X                        |               |                      |

